6.7.3 Pharmacokinetic Endpoints

The following PK parameters for ZN-c5, palbociclib, and metabolites will be estimated by NCA using the software Phoenix® WinNonlin® Version 8.3 (Certara, USA).

Table 5 Pharmacokinetic Parameters

PK Parameter	Definition
Cycle 1 Day 1	
Adjusted R ²	Adjusted coefficient of determination
AUC ₀₋₈	Area under the plasma concentration time curve from 0 to 8 hours post-dose
AUC ₀₋₁₂	Area under the concentration-time curve from the time of dosing to the end of the dosing interval (12 h post-dose for BID dosing; ZN-c5 only)
AUC ₀₋₂₄	Area under the concentration-time curve from the time of dosing to the end of the dosing interval (24 h post-dose for QD dosing)
AUC _{last}	Area under the plasma concentration-time curve from time 0 to time of last quantifiable plasma concentration
AUC _{inf}	Area under the plasma concentration-time curve from time 0 extrapolated to infinity
AUC _{extr}	The proportion of AUC _{0-∞} due to extrapolation from time T _{last} to infinity, expressed as a %
C _{max}	Maximum observed plasma concentration after a single dose administration
C ₀₋₁₂	Concentration at the end of the dosing interval (BID dosing; ZN-c5 only)
C ₀₋₂₄	Concentration at the end of the dosing interval QD dosing only)
T _{max}	Time of maximum observed plasma concentration after a single dose administration
λ _z	Terminal elimination phase rate constant
T _{1/2}	Apparent terminal elimination half life
T _{last}	Time of last observed quantifiable concentration
CL/F ^a	Apparent total plasma clearance after a single dose administration
V _z /F ^a	Apparent volume of distribution after a single dose oral administration
MR ^b	Metabolic ratio of the conversion of a parent drug to its metabolite using AUC ₀₋₁₂ or AUC ₀₋₂₄ as MR = AUC (metabolite)/AUC (parent), for BID dosing or QD dosing, as appropriate.
Cycle 1 Day 15	
Adjusted R ²	Adjusted coefficient of determination
AUC ₀₋₈	Area under the plasma concentration time curve from 0 to 8 hours post-dose
AUC _{tau}	Area under the concentration-time curve from the time of dosing to the end of the dosing interval (tau = 12 or 24 hours)
AUC ₀₋₂₄	Area under the concentration-time curve calculated as 2 × AUC ₀₋₁₂ for the BID dose only.
C _{max,ss}	Maximum observed plasma concentration after multiple dose administration
T _{max,ss}	Time of maximum observed plasma concentration after multiple dose administration
λ _z (Lambda z)	Terminal elimination phase rate constant

PK Parameter	Definition

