T _{1/2}	Apparent terminal elimination half life
T _{last}	Time of last observable quantifiable concentration
C _{trough}	Concentration at the end of the dosing interval (tau = 12 or 24 hours)
C _{ave}	Average steady-state plasma concentration
CL _{ss} /F ^a	Apparent total plasma clearance after multiple dose oral administration
V _{z,ss} /F ^a	Apparent volume of distribution after multiple dose oral administration
MR ^b	Metabolic ratio of the conversion of a parent drug to its metabolite using AUC _{tau} as MR = AUC (metabolite)/AUC (parent), tau = 12 or 24 hours for BID dosing or QD dosing, respectively.
RAUC	AUC accumulation ratio defined as AUC Day 15/AUC Day 1 (where Day 1 AUC ₀₋₁₂ or AUC ₀₋₈ [BID dosing] or AUC ₀₋₂₄ [QD Dosing] and Day 15 AUC ₀₋₈ (BID dosing only) or AUC _{tau} ; tau = 12 (BID dosing) or 24 hours)

^a Determined for parent drug only

^b Determined for palbociclib and its metabolite

C_{max}, C_{max ss}, C₀₋₁₂, C₀₋₂₄, C_{trough}, T_{max}, and T_{max, ss} will be obtained directly from experimental observations. If multiple maxima occur at equal concentrations, the first temporal value will be taken as the C_{max}/C_{max ss} and T_{max}/T_{max, ss}.

T_{1/2}, where determinable, will be calculated as the natural logarithm of 2 divided by the terminal phase rate constant, lambda z (λ_z). The number of data points included in the regression will be determined by visual inspection, but a minimum of 3 data points in the terminal phase, excluding C_{max}/C_{max,ss}, is required to estimate λ_z . In addition, T_{1/2} should be determined with a span ≥ 2 with span defined as the time interval used to determine lambda z (i.e., upper lambda z minus lower lambda z) divided by the T_{1/2}. If this criteria is not met, the T_{1/2} data will be excluded from summary statistics but will listed and flagged.

In order for λ_z -derived parameters (λ_z , V_z/F, V_{ss}/F, and T_{1/2}) to be listed and summarized, the adjusted r² value reported in Phoenix®WinNonlin® must be ≥ 0.8 . In addition, AUC_{extr} must be <20% for Cycle 1 Day 1 PK parameters only (AUC_{inf}). All PK parameters that do not meet these criteria will be listed.

Regression parameters for estimation of λ_z , including the number of time points used, time point range, r-squared, adjusted r-squared, and span will be listed.

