For the purpose of calculating AUC, all missing values will be treated as missing in the PK analysis and excluded from analysis except when they occur at pre-dose (of Day 1), where they will be set to 0. Missing pre-dose values for all other days will be handled on a case-by-case basis and may be imputed using the C_{trough} value for that corresponding dosing interval. If C_{trough} value is missing, the missing pre-dose will be imputed using the lowest concentration value observed for that corresponding dosing interval, if warranted.

All AUCs including partial AUCs (AUC₀₋₈, AUC₀₋₁₂, AUC₀₋₂₄, and AUC_{tau}) will be calculated using the linear trapezoidal method and actual elapsed time values. AUC₀₋₂₄ for the BID dosing will be determined by estimating $2 \times$ AUC₀₋₁₂ for Cycle 1 Day 15. If no PK sample was collected at the 12 or 24 hour post dose for either the BID or QD dosing regimen, one of two approaches will be taken to allow for the determination of AUC₀₋₈, AUC₀₋₁₂, AUC₀₋₂₄ or AUC_{tau}:

- For Cycle 1 Day 1, the 12 or 24 hour post-dose sample will be calculated via an extrapolation method using Phoenix® WinNonlin® standard calculations. If no lambda z is estimated, AUC₀₋₈, AUC₀₋₁₂ or AUC₀₋₂₄ will not be estimated. Moreover, the adjusted r^2 value must be ≥ 0.8 and AUC_{extr} must be <20% for AUC₀₋₈, AUC₀₋₁₂, and AUC₀₋₂₄ to be estimated by extrapolation.
- For Cycle 1 Day 15, the 12 or 24 hour post-dose sample will be imputed using the pre-dose concentration or the minimum observed concentration within that BID or QD dosing interval (if the pre-dose concentration is missing) to obtain the AUC_{tau}.

CL/F on Day 1 will be calculated as Dose (D)/AUC₀₋₁₂ or AUC₀₋₂₄ and CL_{ss}/F on Day 15 will be calculated as Dose (D)/AUC_{tau} (where tau = 12 or 24 hours).

V/F on Day 1 will be calculated as D/(λ * AUC₀₋₁₂ or AUC₀₋₂₄) and V_{z,ss}/F on Day 15 will be calculated as D/(λ * AUC_{tau}) (where tau = 12 or 24 hours).

C_{ave} will be calculated as AUC_{tau}/12 or AUC_{tau}/24 (where tau = 12 or 24 hours).

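### SAP 6.7.3 labels Day 1 CL/F and V/F as single-dose values but divides by a one-interval AUC, so ordinary accumulation can read as a fall in clearance by Day 15

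*SAP*

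**What the plan says.** The formulas are in SAP 6.7.3. For clearance, "CL/F on Day 1 will be calculated as Dose (D)/AUC" over 0-12 h for BID dosing or 0-24 h for QD dosing. For volume, "V/F on Day 1 will be calculated as D/(λ * AUC" over the same interval. Day 15 CLss/F and Vz,ss/F use AUCtau in the same way.

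Table 5 describes the Day 1 clearance as "Apparent total plasma clearance after a single dose administration" and gives Vz/F a matching single-dose description. The Day 1 block also lists AUCinf, "Area under the plasma concentration-time curve from time 0 extrapolated to infinity", but neither formula uses it.

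The formulas apply to both drugs. The lead-in to Table 5 says "The following PK parameters for ZN-c5, palbociclib, and metabolites will be estimated by NCA", and footnote a, "Determined for parent drug only", limits CL/F and V/F to the two parent drugs. All AUCs "will be calculated using the linear trapezoidal method and actual elapsed time values".

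Two quality rules bear on this. First, for the parameters derived from lambda-z, adjusted r-squared must be at least 0.8, and AUCextr "must be <20% for Cycle 1 Day 1 PK parameters only", followed by AUCinf in brackets. Second, where the 12 h or 24 h sample is missing on Day 1, the interval AUC may be extrapolated only if both criteria are met.

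**The concern.** Dose/AUC0-tau equals apparent clearance only at steady state, when the AUC over one interval equals the whole AUC of a single dose. After the first dose, the part of the curve beyond tau is left out. The Day 15 formula is therefore right if steady state has been reached. The Day 1 formula borrows that form under a single-dose label.

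SAP 6.7.3 summarises the parameters by visit, so Day 1 CL/F and Day 15 CLss/F will be reported in parallel. At equal dose their ratio is AUCtau(Day 15)/AUC0-tau(Day 1), which is the accumulation ratio RAUC under another name. A reader could take accumulation for a fall in clearance. There is a reason to compare the visits: Protocol 2.2 reports that CYP3A enzymes metabolise ZN-c5 and that it induced CYP3A4 in hepatocytes from all three donors. A real rise in clearance would be partly offset by the artefact.

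**Working it through.** **No figure to reproduce.** The documents give no CL/F, V/F, AUC ratio or human half-life.

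**Identity.** (Dose/AUC0-tau) / (Dose/AUCinf) = AUCinf/AUC0-tau. V/F carries the same factor because lambda-z cancels. This compares two estimates from the same method. It is not the error against true clearance.

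**Inputs.**
- From SAP 6.5.6: samples at 0, 0.5, 1, 2, 4, 6, 8 and 24 h for ZN-c5. Palbociclib has the same times relative to its own dose. With BID dosing, the 12 h ZN-c5 sample is optional.
- From SAP 6.7.3: linear trapezoid.
- Assumed: one compartment with first-order absorption, ka = 1.5/h, clearance the same on both days, nominal times, lambda-z from the last three points, and half-lives of 4 to 24 h.

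**Model.** With Dose/V = 1, C(t) = ka/(ka - k) x [exp(-kt) - exp(-ka t)], where k = ln 2 / half-life. Day 15 is the superposition of 15 QD or 29 BID doses.

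**Worked case: QD, half-life 8 h.**
- Trapezoid AUC0-24 on Day 1 = 10.664. The tail C(24)/lambda-z adds 1.531, so AUCinf = 12.195.
- AUCextr = 1.531/12.195 = 12.6%.
- Trapezoid AUCtau on Day 15 = 12.298.
- Day 15 CLss/F over Day 1 CL/F as written = 10.664/12.298 = 0.867. On AUCinf it is 12.195/12.298 = 0.992.
- Excess over the AUCinf form = 12.195/10.664 = 1.144.
- True AUCinf = 1/k = 11.542. As-written CL/F over truth = 11.542/10.664 = 1.08. The AUCinf form over truth = 11.542/12.195 = 0.95.

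**QD across half-lives.**

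| Half-life (h) | AUCinf/AUC0-24 | Day 15/Day 1 as written | Day 15/Day 1 on AUCinf | AUCextr |
|---|---|---|---|---|
| 4 | 1.016 | 0.98 | 0.998 | 1.5% |
| 6 | 1.066 | 0.93 | 0.994 | 6.2% |
| 8 | 1.144 | 0.87 | 0.992 | 12.6% |
| 12 | 1.340 | 0.74 | 0.991 | 25.4% |
| 24 | 2.033 | 0.49 | 0.995 | 50.8% |

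The absorption rate hardly matters: at 8 h the as-written ratio is 0.863 with ka = 1.0/h and 0.871 with ka = 3.0/h.

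**BID with the 12 h sample.** As written, the ratio is 0.86 at a half-life of 4 h and 0.73 at 6 h.

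**Against true clearance, QD.** As-written CL/F over truth is 0.89, 0.98, 1.00 and 1.08 at 4, 6, 6.5 and 8 h. The AUCinf form gives 0.87, 0.92 and 0.95 at 4, 6 and 8 h. The straight line from 8 to 24 h overstates the AUC, and at short half-lives this outweighs the missing tail. The two forms are equally far from the truth at about 7.5 h.

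**Reach of the 20% criterion.** Where it applies, AUCinf/AUC0-tau stays below 1/(1 - 0.20) = 1.25. In the model AUCextr reaches 20% at a half-life of about 10.3 h (QD) or 4.9 h (BID with the 12 h sample).

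**The case against.** The strongest reply is that nothing rests on these values and that a careful reader can undo the problem. The formulas are printed, the two visits use different parameter names, and AUCinf and RAUC sit in the same table. SAP 3.3 makes all analyses descriptive, no Day 1 versus Day 15 clearance contrast is planned, and CL/F is not among the PK parameters the protocol names. All of this stands, and it is why the point is minor. It does not make the label correct.

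The reply is also right on three matters of size and scope.

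- A reader might infer that Day 1 clearance is always overstated. The documents do not support that. With the planned QD sampling, the as-written value is too low below a half-life of about 6.5 h and too high above it. AUCinf improves absolute QD accuracy only above about 7.5 h.
- A reader might infer that nothing limits Day 1 CL/F. That is firmer than the text. Where the 12 h or 24 h sample is missing, the AUCextr limit already applies. Where it was collected, the sentence can be read as covering all Day 1 parameters or AUCinf alone.
- The size is entirely assumed. Protocol 2.2 reports no major accumulation in the animal studies, which is compatible with a small effect.

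**Conclusion.** Wrong as written, minor. Two parameters labelled as single-dose values are defined by a steady-state formula, although the quantity the label needs is already planned. What is certain is the identity: relative to the AUCinf form, both are larger by AUCinf/AUC0-tau.

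The size depends on a half-life the documents do not give. Under the assumed model with clearance unchanged, the apparent QD fall by Day 15 is 2% at a half-life of 4 h, 13% at 8 h and 51% at 24 h. For BID with the 12 h sample it is 14% at 4 h and 27% at 6 h. On AUCinf it is 1% or less.

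The conclusion concerns labelling and comparability between visits. It does not show that absolute clearance is biased in a known direction, or that any dose decision or primary endpoint is affected.

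**What to change.** Adopt one of two changes.

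**(a) Change the formulas.** Define Day 1 CL/F = Dose/AUCinf and Vz/F = Dose/(lambda-z x AUCinf). Name both in the existing criteria (adjusted r-squared at least 0.8, AUCextr below 20%) and list the values that fail. Make any Day 1 versus Day 15 comparison only within the same qualifying subjects.

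The same-subject condition matters because restricting Day 1 alone removes slow-clearance subjects from one visit. In a simulation of the QD model (median half-life 8 h, assumed lognormal clearance CV of 30% or 50%), the by-visit geometric mean ratio is 0.85 or 0.83 as written. It is 0.90 or 0.80 if only Day 1 is restricted, and 0.99 for both CVs when paired on AUCinf.

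The cost is two formula edits, since AUCinf is already produced, and a smaller Day 1 summary weighted towards faster clearance. In the same simulation 80% or 70% of subjects qualify at a median of 8 h, and 30% or 37% at 12 h. Absolute accuracy does not improve at short QD half-lives.

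**(b) Change the labels.** Keep the formulas, rename the quantities Dose/AUC0-tau and Dose/(lambda-z x AUC0-tau), and state that they are not single-dose clearance or volume and are not comparable with CLss/F and Vz,ss/F. This needs no new calculation and loses no subjects, but no Day 1 clearance is then reported.

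Under (b), the SAP should still say whether the AUCextr limit covers these Day 1 quantities or AUCinf only. Option (a) settles this by naming them.

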6.7.4 Pharmacodynamic/Biomarker Analysis

All pharmacodynamic/biomarker data will be presented in listings.

Descriptive statistics of Baseline and change in biomarkers will be provided at each sampling time for all subjects, and by dose/cohort (as applicable).

Longitudinal plots will be presented for selected pharmacodynamic/biomarker parameters.

7. ANALYSES PERFORMED BEFORE DATABASE CLOSURE

Interim futility analyses will be conducted in between stages during the Phase 2 Combination, if applicable. The guiding futility and promising criteria for each cohort are presented in [Table 1](#) and the primary analysis is detailed in Section [6.5.2](#).

8. CHANGES FROM METHODS PLANNED IN THE PROTOCOL

In regard to the Monotherapy Phase 2 Efficacy, section 6.1.7 of the protocol state that efficacy in the Monotherapy Phase 2 will be determined by CBR and results will be combined with those from subjects with similar treatment characteristics (2nd/3rd Line therapy) and treated at the same dose level of ZN-c5 in the Monotherapy Expansion arm. The analysis will simply be done by phase.

An additional population not defined in the protocol, the Tumor Response Evaluable Set has been defined for use in efficacy analyses.

In a Protocol Clarification Letter (15 June 2022), it was announced that study has reached the time point where a data cut-off of 18 May 2022 has been established after the primary objectives of the study have

been met. Beyond this cut-off, only limited information including study drug administration, study drug accountability, and non-serious and serious adverse events were collected in addition to any cases of pregnancy, overdose, or medication error. End of treatment information (reason for discontinuation form only [EOT], not the full visit) and Safety Follow-up information (Date of Visit [DOV] form only, not the full visit) were also collected.

Because this cut-off was adopted by the sites at different dates, subjects who were ongoing may have data reported beyond this cut-off date.

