4.4 END OF STUDY DEFINITION

The end of the study is defined as when the last patient on study has completed their last study visit (i.e., last safety follow-up or last disease assessment follow-up, whichever is last).

If the primary objectives of the study have been met or the Sponsor decides to stop the study early, the database may be locked for the purpose of analyzing and reporting data. Subjects may continue to receive ZN-c5 per protocol beyond the data cut-off for database lock if the Investigator and the Sponsor agree that the patient's best interests are served by remaining on study treatment.

Limited information including, but not limited to study drug administration, study drug accountability, and non-serious and serious adverse events will be collected in addition to any cases of pregnancy, overdose, or medication error. Less frequent subject visits might be implemented as per institutional standard of care.

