9.4.7 PLANNED INTERIM ANALYSES

An interim futility analysis will be conducted after Stage 1 accrual for each dose cohort in the Combination Phase 2 and necessary minimum follow-up is complete. The guiding futility criteria are presented in Section 9.2, Sample Size Determination.

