6.5.2 Tumor and Response Evaluations

Tumor and response evaluations, PFS and DOR analyses will be based on the FAS and repeated on the Tumor Response Evaluable Set.

Tumor and response evaluations, PFS and duration of response analyses will be based on the FAS and Tumor Response Evaluable Subjects population. Data will be summarized by dose level in Dose Escalation and by cohort in Dose Expansion, and listed in by-subject listings in the Tumor Response Evaluable Subjects population.

Clinical Benefit Rate (CBR) is the primary endpoint for the Monotherapy Phase 2 and Combination Phase 2 and a secondary endpoint for the Monotherapy Escalation Phase 1, Monotherapy Expansion Phase 1, and Combination Escalation Phase 1. It is defined as the proportion of subjects who have at least one confirmed response of CR or PR (only if subject has measurable disease), or SD \geq 24 weeks (or non-CR/non-PD \geq 24 weeks for subjects with non-measurable disease) prior to any evidence of progression. Subjects who develop PD, intolerable toxicity or death or who discontinue study treatment prior to the first post-Baseline assessment will be classified as non-responders.

A confirmed response of CR/PR means that a response of CR/PR is recorded at one visit and confirmed by repeat imaging at least 4 weeks later with no evidence of progression between confirmation visits.

In case of SD, measurements should have met the SD criteria for a minimum interval of 8 weeks (8 weeks minus the 7-day visit window) following the start of treatment. Similarly, for non-measurable disease, non-CR/non-PD should be maintained for a minimum interval of 8 weeks (8 weeks minus the 7-day visit window) following the start of treatment.

Best overall response (BOR) will be derived for each subject, based on evaluation of response at each tumor assessment visit per investigator assessment using Response Evaluation Criteria in Solid Tumors (RECIST) version 1.1 and reported in the following categories:

- Complete Response (CR)
- Partial Response (PR)
- Stable Disease (SD)
 - SD \geq 24 weeks in duration
 - 8 weeks < SD < 24 weeks in duration
- Non-CR/non-PD
- Progressive Disease (PD)

- Non-Responders (NR)
- Not Evaluable (NE)

Confirmation of PR and CR responses will follow the confirmation process contained in the following table where the best two consecutive time points are considered.

Earlier Best Response (not yet confirmed)	Later Best Response (confirmation)	Best Overall Response
CR	CR	CR

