CR	No CR or missing	SD
PR	CR or PR	PR
PR	SD or PD or missing	SD
SD	NA – no confirmation needed	SD
PD	NA	PD

Responses recorded after initiation of anti-tumor therapy are not used (not evaluable) nor are PD responses after a missed visit [>126 days has elapsed since the last image-based response assessment (or first dose date if no prior response)] up to 24 weeks after C1D1. If the previous evaluable image-based response assessment is more than 24 weeks after C1D1, a PD response is considered to be "missed" if more than 26 weeks (182 days) has elapsed. In the case of stable disease, measurements should have met the stable disease criteria for a minimum interval of 8 weeks (8 weeks minus the 7-day visit window = 49 days) following the start of treatment.

Duration of SD for subjects with best overall response = SD is defined as the time from the day of first study treatment to the start of radiologic disease progression or death. If the subject does not have a radiological disease progression or death, the duration of SD is defined as the time from the day of first study treatment to the date of the last SD assessment. Taking scheduling of imaging into account, a 1 week window will be utilized such that the threshold for 24 weeks will be $23*7 = 161$ [response date – first dose date +1 ≥ 161].

When the investigator is in doubt as to whether progression of disease has occurred and therefore reassesses the subject at a later date, the date of the initial scan should be declared as the date of progression if the repeat scans confirm progression.

Objective Response Rate (ORR) is a secondary endpoint for all cohorts. It is defined as the percentage of subjects with measurable disease who have at least one confirmed response of CR or PR prior to any evidence of progression (as defined by RECIST v1.1). Subjects who develop PD, intolerable toxicity or death or who discontinue study treatment prior to the first post-Baseline assessment will be classified as non-responders.

Data obtained up until progression, or last evaluable assessment in the absence of progression, will be included in the assessment of ORR. However, any complete response or partial response which occurred after a further anticancer therapy was received will not be included in numerator of the ORR calculation.

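### The final CBR analysis sets no minimum follow-up, so stable disease still ongoing before day 161 at the data cut-off counts as non-benefit and can lower the Phase 2 primary estimate

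*SAP*

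**What the plan says.** CBR is the primary endpoint of both Phase 2 parts and a secondary endpoint in the others. SAP 6.5.2 says: "It is defined as the proportion of subjects who have at least one confirmed response of CR or PR" (PR only with measurable disease), or stable disease (SD) of at least 24 weeks, or non-CR/non-PD of at least 24 weeks in non-measurable disease. It is analysed in the FAS, meaning everyone with at least one dose (SAP 5.1), and repeated in the Tumor Response Evaluable Set. It is reported as a simple proportion with a Clopper-Pearson interval.

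For a subject who has neither progressed nor died, "the duration of SD is defined as the time from the day of first study treatment to the date of the last SD assessment". The 24-week threshold is relaxed by one week to 161 days. Scans are due every 8 weeks, within 7 days either way, for the first 24 weeks (Protocol 8.1.1).

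On timing, Protocol 4.4 says: "If the primary objectives of the study have been met or the Sponsor decides to stop the study early, the database may be locked". It gives no length of follow-up. SAP Section 8 then sets the cut-off: "a data cut-off of 18 May 2022 has been established after the primary objectives of the study have" been met. It adds: "Beyond this cut-off, only limited information including study drug administration, study drug accountability, and non-serious and serious adverse events were collected", with a few further items, none of which is a tumor scan. Because sites adopted the cut-off at different dates, "subjects who were ongoing may have data reported beyond this cut-off date".

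The one mention of minimum follow-up is in Protocol 9.4.7. It governs the Combination Phase 2 interim only, which waits until "necessary minimum follow-up is complete", and no number is attached.

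**The concern.** A 24-week endpoint can be scored only when the subject has had the chance to be scanned at about week 24. Under the rules above, someone dosed late who is still in SD at the last recorded scan is neither censored nor put in a class of their own. Once the 8-week SD minimum is met, the only SD category left is 8 to 24 weeks, which does not count as benefit. An unfinished observation is then handled like a failure.

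The SAP treats the same subject differently for PFS. Table 3, situation 5, censors at the last adequate assessment when there is no progression or death by the cut-off.

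The Phase 2 CBR is meant to inform a larger study and the choice among up to three monotherapy doses. It is set beside fulvestrant figures of 40% and 56% (Protocol 9.2.3). A shortfall from incomplete follow-up would enter that comparison, and the exact interval would not reflect it. Doses randomized side by side should be affected about equally; doses or parts opened later would be affected more.

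**Working it through.** **1. The plan's own precision.** Protocol 9.2.3 states ±12 points for an exact 95% interval at 75 subjects per dose and a CBR of 40–50%. Clopper-Pearson gives:
- 30/75 = 40.0%: 28.9% to 52.0% (−11.1/+12.0)
- 38/75 = 50.7%: 38.9% to 62.4% (−11.8/+11.7)

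The stated figure reproduces. It assumes that every subject's 24-week status is known.

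**2. Which scan can qualify.** The latest in-window week-16 scan is 16 × 7 + 7 = 119 days after first dose, or day 120, short of 161. The week-24 scan is 168 days after first dose (day 169), with a window from day 162 to day 176. On schedule, SD can qualify only through the week-24 scan.

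**3. First-dose dates that allow it.** The SAP test is scan date − first dose + 1 ≥ 161.
- Scans up to 18 May 2022: 18 May 2022 − 160 days = 9 December 2021.
- Whole week-24 window closed by the cut-off: 18 May 2022 − 175 days = 24 November 2021.
- If a site kept scanning until the clarification letter of 15 June 2022, which is 28 days after the cut-off: 15 June 2022 − 160 days = 6 January 2022.

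**4. Size of the effect.** Let f be the share of the denominator still in SD with a last scan before day 161 because follow-up stopped. Let q be the chance that such a subject would have reached day 161. Then

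expected CBR = true CBR − f × q.

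Both terms are zero or positive, so this source of error is never upward. One affected subject who would have reached 24 weeks costs 1/75 = 1.33 points; nine cost 9/75 = 12 points, the whole stated half-width. The documents give neither f nor q, so the values below are assumptions:

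| Assumed f | q = 0.5 | q = 0.9 |
|---|---|---|
| 0% | 0 | 0 |
| 5% | −2.5 points | −4.5 points |
| 10% | −5 points | −9 points |
| 20% | −10 points | −18 points |

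At n = 75 and a true CBR of 40–50%, coverage of the nominal 95% interval is about 96% with no bias. It is about 94% at −2.5 points, 87–89% at −5 and 59–64% at −10.

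**5. How many could be late.** Assume even accrual from a start date to g days before the cut-off, T days in all. The share dosed after 9 December 2021 is (160 − g)/(T − g). Protocol 10.5 offers three candidate start dates: v6.0 (20 April 2021, T = 393), v5.0 (14 September 2020, T = 611) and v4.0 (14 February 2020, T = 824), which added Monotherapy Phase 2.

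| g | from v6.0 | from v5.0 | from v4.0 |
|---|---|---|---|
| 0 | 160/393 = 41% | 160/611 = 26% | 160/824 = 19% |
| 90 | 70/303 = 23% | 70/521 = 13% | 70/734 = 9.5% |
| 160 or more | 0% | 0% | 0% |

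These shares are ceilings on f: late subjects who had already progressed, or had a confirmed response, are not affected.

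**The case against.** The strongest reply is that no bias has been shown. The cut-off followed attainment of the primary objectives. For Phase 2 that objective is CBR, which itself rests on 24-week SD, so an arbitrary truncation looks unlikely. Ongoing subjects may have scans after 18 May 2022, and the SAP contains no rule discarding them. The SAP never says in words that ongoing SD is a failure, and leaving unreached 24-week SD uncounted can be defended as conservative. SAP 6.5.3 already gives Kaplan-Meier PFS at 6 months with censoring, and best overall response separates SD above and below 24 weeks.

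Much of this stands. A reader might infer that CBR in this trial is biased downward, or that about 40% of subjects lacked follow-up. The documents support neither reading: there are no first-dose dates and no counts of ongoing SD, and the 41% figure needs accrual to begin only at v6.0 and run to the cut-off. Nor is 9 December 2021 a hard limit if later scans count.

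Four things remain:
- Meeting the objectives is not a follow-up rule. Combination Phase 2 CBR is one of those objectives, yet SAP 5.2 still treats that part as possibly not executed.
- Later scans depend on when each site adopted the cut-off, and the SAP does not say whether they count toward CBR.
- The Tumor Response Evaluable Set does not help. One post-baseline assessment is enough to enter it, so a subject with a single week-8 SD scan is included and scored as non-benefit.
- Six-month PFS is a different quantity. Its time point is 6 × 30.4375 = 183 days rather than 161, and a confirmed response followed by progression before week 24 is a benefit for CBR but an event for PFS.

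**Conclusion.** The gap is in the text: no minimum follow-up is set for the final CBR, and ongoing SD with a last assessment before day 161 sits in the denominator without access to the numerator. That scoring follows from the definitions; the SAP does not state it outright. The test is the date of the last SD assessment, not time on study. A subject past 23 weeks whose week-24 scan is not yet recorded is also affected, and one with an earlier confirmed CR or PR is not.

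The effect can only lower CBR. It is zero if every subject was first dosed early enough for a week-24 scan to be recorded. Otherwise it is 1.33 points per affected subject at n = 75, or −2.5 to −18 points under the assumed f of 5–20% and q of 0.5–0.9. The true size cannot be determined from the documents.

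A reader might also conclude that the FAS should be replaced as the basis of the reported CBR. That goes too far. The FAS is the protocol's efficacy set, and restricting it could cost many subjects: with accrual from v6.0 up to the cut-off, 175/393 = 44.5% would drop out, leaving about 42 of 75 and a half-width near ±16 points. A supplementary analysis is justified; a new primary basis is not.

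**What to change.** Keep the FAS CBR as the main analysis. In SAP 6.5.2:

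- Add a supplementary CBR with exact 95% interval, per dose level and study part, in all FAS subjects first dosed at least 175 days before the cut-off (on or before 24 November 2021). Count early dropouts in that group as non-benefit. Selection then depends only on the first-dose date, not on outcome.
- Report, per dose level, how many subjects were first dosed after 24 November 2021, and how many were progression-free with a last assessment before day 161.
- State whether scans dated after 18 May 2022 count toward CBR, and apply the answer to all sites alike.

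The cost is one derived flag and one extra table, with no new data. The supplementary interval will be wider where a cohort enrolled late, and a few subjects dosed between 25 November and 9 December 2021 who did reach day 161 will be left out of it. If everyone was dosed by 24 November 2021, the two estimates coincide and that can be stated in one line.
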